The primary exposure assessment will be based on the contaminant levels in the drinking water serving the person's residence (or workplace location for civilian employees). Each month of residence (or civilian employee's workplace) will be linked to the estimated levels of contaminants in the drinking water serving that location for that month. The person's cumulative exposure will be calculated as well as the average exposure, maximum level of exposure, and exposure duration. These exposure metrics will also be categorized *a priori* into meaningful categories (based on the contaminant level distribution) as well as categorized using a smoothing technique (e.g., LOESS and/or splines). Other possible exposures (i.e., to contaminated drinking water in field training, at the work location of the active duty personnel, or occupational exposures to solvents during the active duty individual's work service) will be explored if sufficient information is obtained from the health survey instrument and personnel databases to assess these exposures.

The military occupation specialty (MOS) code for active duty personnel and the occupation code for civilian employees will be obtained from the DMDC data. Based on discussions with knowledgeable former Marines and current occupational hygiene employees at Camp Lejeune, ATSDR obtained information on the types of chemicals used in various military and civilian occupations at the base. The MOS and civilian occupation codes will be linked to this information to assess potential occupational exposures to chemicals at the workplace.

The locations of workplaces (and the water system serving these locations) will be

based on discussions with knowledgeable former Marines and current staff at Camp Lejeune as well as on survey information provided by the respondent. Drinking water in the field was provided in tanks and “buffaloes”; the water could have come from anywhere on base, but most likely came from Hadnot Point. For this reason, it was deemed possible that all active duty personnel were exposed to contaminated drinking water at Camp Lejeune during their field training and this will be addressed in the data analysis.

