Determining the water quality at residences and workplaces at Camp Lejeune is simplified by the fact that, within each water system, the water was completely mixed so all locations served by a water system received similar levels of contamination. It is therefore only necessary to determine in which broad area of the base the residence or workplace is located. The information from the family housing records (for married active duty personnel), the unit identification codes (for single active duty personnel), the MOS code (for active duty workplaces), and the occupation code (for civilian employees), when combined with the information obtained from command chronologies, discussions with knowledgeable former Marines and current base staff, and survey information provided by the respondent, should be sufficient to identify the area of the base where a residence or workplace was located and to determine which water system served that residence or workplace.

Because of uncertainties and variabilities concerning the amount of water each individual routinely consumed (i.e., by ingestion, inhalation and dermal routes), the source of water in the field, the amount of time an individual routinely spent outside the base or in other parts of the base besides the residence, exposure misclassification bias is likely. This bias should be non-differential, i.e., not associated with disease status. However, non-

differential exposure misclassification can distort exposure-response relationships. One approach to reduce the effects of this bias on the exposure-disease relationship is to compare the group with the most certainty of being the highest exposed to the unexposed group. To assess the possible impact of this bias, sensitivity analyses will be conducted assuming different values for the sensitivity and specificity of the exposure classification.

Morbidity Study Population

Persons eligible for the morbidity study are those with accurate and complete addresses who were:

1. Marines and Navy personnel identified from the DMDC computerized personnel database as having been stationed at Camp Lejeune anytime during the period June 1975- December 1985;
2. civilians identified from the DMDC computerized personnel database as having worked at Camp Lejeune anytime during the period December 1972 to December 1985;
3. respondents and their children (who were born prior to 1986 and who are now adults) included in the 1999-2002 ATSDR survey;

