All comparisons will be “internal comparisons” where the Camp Pendleton cohorts will be the unexposed group. If those at Camp Lejeune whose residences were not served by contaminated water have a similar risk for a specific disease as the Camp Pendleton cohorts, then they will be included along with the Camp Pendleton cohorts in the unexposed group. If their risks are observed to be different, then an indicator variable will be included in the analyses that distinguishes the unexposed at Camp Lejeune from the unexposed at Camp Pendleton.

Since drinking water in the field was provided in tanks and “buffaloes” that could have come from anywhere on base, but most likely came from Hadnot Point, it was deemed possible that all active duty personnel were exposed to contaminated drinking water at Camp Lejeune during their field training. This is the primary reason why unexposed comparison groups from Camp Pendleton are necessary. In the subsequent analyses, it will be assumed that all active duty Marines had the potential for drinking water exposures in the field. A variable for field drinking water exposure (based on the contamination levels at Hadnot Point during the period when the individual was stationed at the base) will be added to the Poisson (or Cox) regression models.

Sensitivity Analyses of Selection and Information Biases

For selection bias (or non-response bias) to be present, participation rates must

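### Camp Lejeune active duty members can join the pooled unexposed reference on residence alone, even if their workplace was on a contaminated water system

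*Protocol*

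**What the plan says.** All statements are in the Protocol.

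- **Exposure Assessment, primary metric.** Exposure is taken from the water serving the "residence (or workplace location for civilian employees"). The linkage follows the same rule: "Each month of residence (or civilian employee's workplace) will be linked to the estimated levels of contaminants".
- **Exposure Assessment, other exposures.** Water "at the work location of the active duty personnel, or occupational exposures to solvents during the active duty individual's work service) will be explored if" enough information comes from the survey and personnel databases.
- **Exposure Assessment, data sources.** Housing records, unit codes, the MOS code (listed for active duty workplaces), command chronologies, knowledgeable informants and the survey, taken together, "should be sufficient to identify the area of the base where a residence or workplace was located" and so which water system served it.
- **Data Analysis, reference group.** Camp Pendleton is the unexposed group. If "those at Camp Lejeune whose residences were not served by contaminated water" have a similar risk for a disease, "then they will be included along with the Camp Pendleton cohorts in the unexposed group". If the risks differ, an indicator variable separates the two unexposed groups. A field-water variable at Hadnot Point levels is added in subsequent analyses.
- **Data Analysis, civilians.** They are analyzed separately, because their main exposure is at the workplace. A combined analysis is optional.
- **Table 1.** The planned reference adds the Lejeune unexposed to Pendleton in every column.

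**The concern.** The condition for entering the pooled reference names residence and nothing else. An active duty member housed off base or on a clean system, but assigned to a workplace on Hadnot Point water, meets it. Such people are foreseeable: the Rationale section reports that the 2005 panel listed adults who lived off base and worked on base.

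If they are pooled with Pendleton, the reference rate contains some of the effect under study, and every RR measured against it shrinks toward 1. The only gate is the similar-risk condition, which has no stated criterion. The field-water variable does not close the gap. It follows Hadnot Point levels while the member was stationed on base, so it does not separate a contaminated workplace from a clean one, and it does not change who is in the reference group.

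**Working it through.** **Inputs from Table 1.** Respondents: 160,550 from Lejeune and 39,000 from Pendleton. Two-sided alpha 0.10, power 90%. In the 20% column the Lejeune unexposed number U = 0.20 × 160,550 = 32,110, the pooled reference is n0 = 39,000 + 32,110 = 71,110, and the exposed are n1 = 128,440.

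**Assumed, not in the documents.** f is the share of U with contaminated workplace water. e is the fraction of the full excess risk that workplace water carries (e = 1 is full effect).

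**Step 1: reproduce the plan's figure.** I used the two-proportion sample size formula with pooled variance under the null and a continuity correction, and solved for RR at p0 = 0.08%. The result is 1.563 against the stated 1.57. All 40 cells of Table 1 agree within 0.022. The table's reference therefore does include the Lejeune unexposed.

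**Step 2: dilution when pooled.** The misclassified share of the reference is s = fU/n0, and

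observed RR = RR / [1 + s·e·(RR − 1)].

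| f | e | s | true RR 2.0 seen as | true RR 1.5 seen as |
|---|---|---|---|---|
| 0.50 | 1 | 16,055/71,110 = 0.226 | 2/1.226 = 1.63 | 1.5/1.113 = 1.35 |
| 0.25 | 1 | 8,027.5/71,110 = 0.113 | 2/1.113 = 1.80 | 1.5/1.056 = 1.42 |
| 0.25 | 0.5 | 0.113 | 2/1.056 = 1.89 | 1.5/1.028 = 1.46 |

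Table 1's population includes civilians, who are outside this analysis. With Pendleton Marines only (50,000 × 0.65 = 32,500) and the same U, the first entry becomes 2/(80,665/64,610) = 1.60. The number of active duty unexposed at Lejeune is not given.

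**Step 3: can the similar-risk condition catch it?** The plan states no test, so I assumed a two-sided 0.10 comparison of 32,110 Lejeune unexposed with 39,000 at Pendleton. The Lejeune rate is p0[1 + f(RR − 1)], with f = 0.5 and e = 1. Power to find the Lejeune rate higher:

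| Incidence p0 | true RR 1.5 (Lejeune rate 1.25 times) | true RR 2.0 (Lejeune rate 1.5 times) |
|---|---|---|
| 0.02% | 0.12 | 0.22 |
| 0.08% | 0.23 | 0.52 |
| 0.16% | 0.35 | 0.77 |
| 0.24% | 0.46 | 0.90 |

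For rare cancers the contaminated stratum would usually look similar and be pooled. For the commoner cancers with a large effect the check would usually work.

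**Step 4: cost of removing them.** Use the Step 1 formula in the 20% column and remove a share f of U from the reference.

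| Removed from U | min. detectable RR at 0.08% | at 0.02% |
|---|---|---|
| none | 1.56 | 2.30 |
| one quarter | 1.59 | 2.37 |
| one half | 1.62 | 2.46 |
| all (Pendleton only) | 1.72 | 2.73 |

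**The case against.** The case on the other side has real weight.

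- **Pendleton is the default reference and pooling is conditional.** The protocol recognizes that all active duty personnel may have been exposed through field water, and gives this as the main reason for having Pendleton. This stands, and it limits the problem to diseases for which pooling takes place.
- **When the indicator is used, the exposed-versus-Pendleton RR is not diluted.** This stands. Nothing in the text says that the indicator would be read as a mere base difference.
- **Misclassification is acknowledged.** The Exposure Assessment section names time spent elsewhere on base, plans analyses over assumed sensitivity and specificity, and proposes comparing the most certainly highest exposed with the unexposed. This stands in part: those analyses gauge the error afterwards, and the last comparison still needs a clean unexposed group.
- **The magnitudes rest on assumed shares and effects.** This stands. They are illustrations.

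A reader might infer more: that the protocol treats active duty workplace water as no exposure at all, and contradicts itself by counting the same water for civilians. The documents do not support that. The residence rule applies to the primary metric, workplace water is listed for exploration, and civilians are modelled separately, so the two codings meet only in the optional combined analysis. Nor do the two statements on data conflict outright: one is an expectation and the other a condition. Keeping the less directly documented location secondary is defensible.

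**Conclusion.** The point holds for the pooling rule. As written, it can place active duty members with contaminated workplace water in the reference group, on a similarity condition that has no criterion and would be weak for rare cancers. In the 20% column of Table 1, and only if pooling occurs, a true RR of 2.0 would be seen as 1.63 to 1.80 for shares of one half to one quarter at full effect, and as about 1.89 for one quarter at half the excess risk. The full-effect figures are upper bounds on the dilution at each share. The true share and effect are unknown, and a small share or a weak workplace effect would make the bias minor.

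It does not follow that the primary exposure metric is wrong or that a workplace term must enter the primary model. That is a debatable design choice. The reference group can be cleaned without it, using data the plan already expects to hold.

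**What to change.** In Data Analysis, restrict pooling with Camp Pendleton to active duty members whose residence and identified workplace were both on uncontaminated systems. Keep members with a known contaminated workplace, and those whose workplace cannot be located, out of the pooled reference as two separate levels. A workplace-water term for active duty, built with the planned workplace linkage, can be a sensitivity analysis.

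The cost is wording, and use of the MOS, unit and survey information already planned. The pooled reference becomes smaller. In the 20% column at 0.08% incidence, the minimum detectable RR rises from 1.56 to 1.59 if one quarter of the Lejeune unexposed are removed, to 1.62 if half are, and to 1.72 at most if none can be pooled. At 0.02% the corresponding rise is from 2.30 to 2.37, 2.46 and 2.73.

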
World Health Organization (WHO). Trichloroethene in Drinking-water: Background document for development of WHO Guidelines for Drinking-water Quality. 2005.

DRAFT

Table 1. Minimum Detectable Incidence Rate Ratio (“RR”)

% disease in the unexposed	Cancers*	10% unexposed**	20% unexposed**	25% unexposed**	30% unexposed**
.08%	Brain, Leukemias	1.62	1.57	1.56	1.55
.22%	Colon & Rectum	1.35	1.33	1.32	1.32
.02%	Esophagus, Larynx, Multiple Myeloma	2.43	2.32	2.29	2.26
.09%	Kidney, Oral	1.58	1.53	1.52	1.51
.03%	Liver	2.11	2.02	2.00	1.98
.20	Lung, Thyroid	1.37	1.34	1.34	1.33
.24%	Melanoma	1.33	1.31	1.30	1.30
.16%	Non-Hodgkin’s lymphomas	1.42	1.39	1.38	1.37
.04%	Pancreas, Stomach	1.93	1.86	1.84	1.82
.06%	Urinary Bladder	1.73	1.67	1.66	1.65

* More than one cancer type may have the same estimated incidence in the unexposed.

** % unexposed among those who resided, worked or were stationed at Camp Lejeune. This group is then added to those who were stationed at Camp Pendleton. For example, assuming 247,000 from Camp Lejeune and 60,000 from Camp Pendleton, and assuming a 65% participation rate, then approximately 160,550 from Camp Lejeune and 39,000 from Camp Pendleton will respond to the survey. The “10% unexposed” includes the 39,000 from Camp Pendleton and 10% of the Camp Lejeune participants (i.e., 16,055), for a total of 55,055 unexposed.

The **minimum detectable risk ratio** was calculated based on a type 1 error of .10 (equivalent to a 90% confidence interval or a p-value, two-tailed of .10) and a type 2 error of .10 (equivalent to 90% statistical power).

The incidences in the unexposed group were estimated based on the age-specific, 1999-2004 U.S. cancer incidence rates (all genders and race/ethnicity groups combined) from the National Program of Cancer Registries, CDC and the following assumptions:

1. The health survey instrument would be mailed to approximately 307,000 including 60,000 from Camp Pendleton;
2. Participation rate would be 65%
3. The average participant first resided or worked at the base at age 19 in 1980. (This assumption is based on the fact that the majority of those receiving the survey were active duty Marines and Navy personnel who were stationed at the base anytime between 1975 and 1985 and who started active duty in 1975 or later.)
4. Follow-up begins 10 years after first resided or stationed at the base (i.e., a 10-year latency period)
5. The follow-up period for the average participant therefore begins in 1990 (age 29) and continues until 2008 (age 47).
6. Cancer rates for the unexposed are similar to national rates.

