For a sample size calculation, the values of the alpha error, beta error, and minimum meaningful effect size are selected, and the required sample size is calculated. However, since the number of exposed subjects cannot be increased, and the alpha and beta errors should be set as low as possible, the only parameter that can vary is the meaningful effect size. Table 1 provides estimates of the minimum meaningful effect size (i.e., the incidence rate ratio or “RR”) for various cancers assuming an alpha error of 0.10 (i.e., equivalent to using a 90% confidence interval), a beta error of 0.10 (i.e., 90% statistical power), and various estimates of exposure prevalence in the surveyed population. The expected number of cancers provided in Table 1 are based on the age-specific 1999-2004 U.S. cancer incidence rates (all genders and race/ethnicity groups combined) from the National Program of Cancer Registries and estimates of the person-time contributed to each 5-year age grouping by the surveyed population after a 10-year lag to account for a latency period. The table assumes that the survey is sent to 247,000 from Camp Lejeune and 60,000 from Camp Pendleton and that the overall response rate for the survey is 65%. For most cancers, the minimum detectable RR is less than 2.0.

Reimbursement

No remuneration will be offered to participants.

Human Subjects and Confidentiality

The Centers for Disease Control and Prevention (CDC) and ATSDR Privacy Act

Officer has reviewed this Institutional Review Board (IRB) application and has determined that the Privacy Act is applicable. The contractor must verify full names and locating information on respondents because certain information (date of birth, social security number) must be verified or obtained in order to conduct the study and analyze the data. Privacy Act clauses will be included in the contract to protect against inappropriate data disclosures. Records will become part of the ATSDR Privacy Act system of records 09-19-0001, "Records of Persons Exposed or Potentially Exposed to Toxic or Hazardous Substances."

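### Table 1's 90% power assumes unexposed Camp Lejeune respondents are pooled with Camp Pendleton; where the plan's pooling condition is not met, power at the printed RRs averages about 82% (10% column) to 71% (30% column)

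*Protocol*

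**What the plan says.** - **Protocol, Table 1, second footnote.** It expects "approximately 160,550 from Camp Lejeune and 39,000 from Camp Pendleton will respond to the survey". Each column takes a percentage of the Lejeune respondents as unexposed, and "This group is then added to those who were stationed at Camp Pendleton". The worked example for the 10% column is 39,000 + 16,055 = 55,055 unexposed.
- **Protocol, Table 1, notes.** Type 1 error is 0.10, "equivalent to a 90% confidence interval or a p-value, two-tailed of .10", and type 2 error is 0.10. One set of national cancer rates is assumed for all unexposed people.
- **Protocol, Data Analysis.** Comparisons are internal, "where the Camp Pendleton cohorts will be the unexposed group". Lejeune members whose residences did not receive contaminated water are added for a given disease only if their risk resembles that at Pendleton. If it does not, an indicator variable keeps the two unexposed groups apart. On possible field-water exposure of all active duty personnel, the section says: "This is the primary reason why unexposed comparison groups from Camp Pendleton are necessary".
- **Protocol, Sample Size, Power, and Precision of Risk Estimates.** "For most cancers, the minimum detectable RR is less than 2.0".
- **Protocol, Expert Panel.** The panel considers the power calculations when it recommends how the study should proceed.

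**The concern.** The power table and the analysis rule do not use the same reference group. Table 1 always pools. The Data Analysis section starts from Camp Pendleton and decides on pooling later, one disease at a time. Neither Table 1 nor the sample size section says that the printed RRs hold only on the pooling branch, and there is no Pendleton-only column.

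The outcome of the similarity check cannot be taken for granted. At an incidence of 0.02%, about 3 cases are expected among 16,055 unexposed Lejeune respondents (0.0002 × 16,055 = 3.2) and about 8 among 39,000 at Pendleton (0.0002 × 39,000 = 7.8). The group being pooled is also one for which the Protocol itself raises possible field exposure.

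At stake is how the expert panel, and later readers of null results, judge what the study could have detected. The columns with the smallest printed RRs are those that lose most if pooling is not made.

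**Working it through.** **Inputs, all from Table 1 and its notes.** Lejeune respondents 160,550; Pendleton respondents 39,000; two-sided alpha 0.10 (z = 1.645); power 90%; incidence p0 in the unexposed and printed RR by row and column. With unexposed share u, the exposed group is n1 = 160,550 × (1 − u). The reference n0 is 39,000 + 160,550 × u as tabulated, or 39,000 if Pendleton stands alone.

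**Formula.** Two proportions, pooled variance, continuity correction. Let p1 = RR × p0, d = p1 − p0, k = n1/n0, pbar = (p0 + k·p1)/(1 + k).

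- Continuity correction: c = (k + 1)/(2·k·d); n* = (n0 − c)²/n0.
- z = [d·√(k·n*) − 1.645·√((k + 1)·pbar·(1 − pbar))] / √(k·p0·(1 − p0) + p1·(1 − p1)); power = Φ(z).

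**Step 1: reproduce Table 1.** Brain/leukemias, p0 = 0.0008:

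- 10% column, RR 1.62: n0 = 55,055, n1 = 144,495, c = 1,392, n* = 52,306; z = (0.18377 − 0.10655)/0.05824 = 1.326; power 90.8%.
- 30% column, RR 1.55: n0 = 39,000 + 48,165 = 87,165, n1 = 112,385, c = 2,018, n* = 83,176; z = (0.14409 − 0.08052)/0.04764 = 1.335; power 90.9%.

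All 40 cells give 90.0% to 91.9%, and all 40 detectable RRs fall within 1.0% of the printed ones. Without the continuity correction the same cells give 91.0% to 92.8%, so the corrected formula is the right like-for-like tool.

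**Step 2: same formula, same RRs, Pendleton alone (n0 = 39,000).**

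- 10% column, RR 1.62: c = 1,280, n* = 36,482; z = (0.18235 − 0.12303)/0.06524 = 0.909; power 81.8%.
- 30% column, RR 1.55: c = 1,531, n* = 35,999; z = (0.14172 − 0.10871)/0.05951 = 0.555; power 71.0%.

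Over all ten rows:

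| Column | Power, pooled reference | Power, Pendleton alone: range (mean) |
|---|---|---|
| 10% | 90.0–91.0% | 79.6–82.6% (81.5%) |
| 20% | 90.4–91.6% | 72.7–77.3% (75.0%) |
| 25% | 90.4–91.6% | 70.4–75.1% (72.9%) |
| 30% | 90.5–91.9% | 67.9–73.9% (70.9%) |

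**Step 3: RR detectable at 90% power.**

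| Cancer | Printed, 10% / 30% | Pendleton alone, 10% / 30% |
|---|---|---|
| Brain, leukemias | 1.62 / 1.55 | 1.71 / 1.74 |
| Non-Hodgkin's lymphomas | 1.42 / 1.37 | 1.48 / 1.49 |
| Urinary bladder | 1.73 / 1.65 | 1.85 / 1.88 |
| Pancreas, stomach | 1.93 / 1.82 | 2.09 / 2.13 |
| Liver | 2.11 / 1.98 | 2.30 / 2.35 |
| Esophagus, larynx, multiple myeloma | 2.43 / 2.26 | 2.70 / 2.77 |

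**Step 4: the below-2.0 statement.** Table 1 lists 16 cancer types. Printed RRs are below 2.0 for 12 of them in the 10%, 20% and 25% columns and for 13 in the 30% column, where liver is 1.98. With Pendleton alone the count is 10 in the 10% and 30% columns: pancreas, stomach, liver, esophagus, larynx and multiple myeloma are above 2.0.

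**The case against.** The strongest reply is that Table 1 contains no miscalculation. Its sums are right, its footnote openly describes the pooled group, and it assumes one rate for all unexposed people. If that assumption is true, the similarity check should usually allow pooling, and Table 1 then describes a planned analysis. This stands, and it makes the loss conditional. It does not excuse presenting only the favourable branch without naming the condition.

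Four stronger readings are tempting, and the Protocol does not support them:

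- *That the study lacks 90% power at every printed RR.* This is so only where pooling is not made.
- *That the trend across columns is wrong.* Detectable RRs fall as the unexposed share rises because the pooled reference grows, which is correct for the tabulated design. The trend reverses only when the reference is fixed at 39,000 and the exposed group shrinks.
- *That the sentence about most cancers is false.* With Pendleton alone, 10 of 16 types remain below 2.0.
- *That field water leaves no unexposed Lejeune group.* The Exposure Assessment section bases primary exposure on residence (workplace for civilians), and Data Analysis handles field water by an added variable in later models. If those respondents were counted as exposed, they would enlarge the exposed group: 160,550 against 39,000 gives detectable RRs of 1.70 at 0.08% and 2.28 at 0.03%.

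One further caveat stands. Civilians are to be analysed separately, and the Pendleton sample is 50,000 Marines and 10,000 civilians, which at 65% gives 32,500 and 6,500. The 39,000 keeps Table 1's own merging of the two, so the Pendleton-only figures isolate the effect of pooling and are not a full power calculation for each planned analysis.

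**Conclusion.** The point holds in conditional form. Table 1 states 90% power for a pooled reference group without saying that the analysis plan pools only when a disease-specific condition is met. Where it is not met, power at the printed RRs falls by roughly 9 points in the 10% column (mean 90.6% to 81.5%) and 20 points in the 30% column (90.9% to 70.9%), and the detectable RRs rise as shown. The conclusion that most listed cancers have a detectable RR below 2.0 survives.

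These figures keep Table 1's 65% participation, incidences, alpha and combined military and civilian population. They also assume that the pooled-variance, continuity-corrected formula is the one behind Table 1; the Protocol does not name its formula, but this one matches all 40 cells.

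**What to change.** 1. Add to Table 1 the minimum detectable RRs with the 39,000 Camp Pendleton respondents alone as the reference, for the same four exposure shares.
2. Label the present columns as applying only if unexposed Lejeune respondents are pooled with Pendleton under the rule in Data Analysis.
3. In the sample size section, cite both sets of figures and note that pancreas and stomach are below 2.0 only with pooling.
4. State the formula used, so that the expert panel can repeat the calculation.

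The cost is one recalculated table and a few sentences. The design, the mailing and the number of participants do not change. The drawback is that the stated detectable RRs become less favourable.
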